### 5. Background and rationale for study

#### 5.1 Background

Multidrug resistant (MDR) bacterial infections are a leading cause of morbidity, death, and healthcare-associated costs. Nowhere is this more important than in the intensive care unit (ICU), where over half of all infections are MDR^4 and where sepsis from MDR bacteria confers 10-20% absolute increased mortality.

This project hypothesizes that antibiotic resistance in the ICU is a problem of the human gastrointestinal microbiome, which is the critical reservoir for the bacteria and plasmids that encode antibiotic resistance genes. The normal gut microbiota prevents colonization and subsequent infection with MDR organisms through competition for scarce resources and other mechanisms. In the setting of critical illness, normal colonization resistance is lost and there are no currently available therapies to restore it.

Specific gut bacteria contribute to colonization resistance. ICU patients have low levels of butyrate and other short chain fatty acids (SCFAs) which are derived from dietary fiber by anaerobic bacteria primarily within the Clostridial Clusters IV and XIVa (e.g., *Faecalibacterium prausnitzii*). SCFAs moderate colonic inflammation, enlarge the pool of regulatory T cells, and

contribute to the thickness of the colonic mucus layer and pathogen resistance. During critical illness, levels of SCFA-producing bacteria and SCFAs are low, and these levels further decline with antibiotic treatment. Loss of SCFA-producing bacteria correlates with an increase in colonization with vancomycin-resistant *Enterococcus* and other antibiotic-resistant pathogens. We believe that preservation of SCFA-producing bacteria during critical illness is of major importance and can prevent the proliferation of colonizing organisms with antimicrobial resistance.

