## 9.2. Rationale for the selection of duration and dose.

9.2.1. Rationale for duration. Inulin will be given for 7 days with the primary outcomes adjudicated after 3 days. The Day 7 data will be used to test whether an effect can be extended or whether a delayed effect is present. In our cohort data, 84/126 (67%) new infections occurred within 3 days and 97/126 (77%) within 7 days. This shows that any ICU-based intervention seeking to prevent infections must work quickly if it is to be effective. Meanwhile, our preliminary cohort data suggests that fiber can have an impact even within this short timeframe (Figure 3). A final assessment will be made on the day of hospital discharge in subjects who are to be discharged prior to Day 14.

9.2.2. Rationale for dose. In the ambulatory setting, inulin impacts SCFA producer levels at doses of 12 to 16 g/day, with biologic effects relevant for ICU patients (e.g., decreases in serum LPS and CRP). Approximately 16 g/day therefore represents the minimum dose at which an effect *might* be seen; this was selected for the low dose arm of the study. However, patients in these ambulatory studies were not critically ill and did not receive antibiotics. It is possible that inulin will have lesser effects in the ICU compared to the ambulatory setting, and logical to test higher doses. To select a maximum study dose, we referenced our own experience with dietary fiber in the prospective cohort and published tolerability data from ICU studies of inulin-like prebiotic fiber. In our prospective ICU cohort, 30 g/day was the maximum observed dose of dietary fiber, and was not associated with any intolerance. In published literature, O’Keefe *et al.* reported tolerance up to a maximum of 36 g/day wheat dextran in the ICU. We therefore selected 32 g/day for the high dose study arm because it lies between these values and is exactly double a dose with proven biologic activity.

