## 9.4. Documentation of administration of the intervention

The study team will work with the treating ICU team to ensure that the study drug is delivered in a timely manner. The time and dose of each medication administration will be documented at each study assessment by referring to the documentation of medication administration within the

electronic medical record (EMR). Patients will be enrolled with a goal of administering the intervention within 24 hours of ICU admission and it will be considered a protocol deviation if the intervention is administered more than 48 hours from ICU admission.

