10.3.4. *Culture-proven MDR infections through ICU Day 30.* Antibiotic-resistant infections will be defined as those showing all of the following: (1) site-specific symptoms or signs of infection, (2) initiation of targeted antimicrobials by the treating ICU team, and (3) molecular diagnostics or cultures showing an MDRO as adapted from the CDC and NHSN and previously used by our group (**Table 4**). Rates of infections will be compared between intervention groups as a sum total, and separately for 3 distinct periods: the intervention period of Day 0 to 7, the Day 7 to 30 period, and the Day 30 to 6 month period.

**Table 4. Criteria used to adjudicate culture-proven MDR infections for.** Criteria based on CDC/NHSN guidelines.

Criteria	Operationalization	Example
1. Site-specific symptoms or signs of infection.	
 
• Pulmonary: documentation of new or worsening cough or imaging consistent with an infection
 
• Urinary: fever, dysuria, increased urinary frequency, flank pain, mental status changes, or hypotension and clinical exclusion of other causes for infection.
 
• Bloodstream: clinical evidence of a bloodstream infection (fever, chills, or hypotension) without alternative sources for infection
 
• Stool: documentation of new loose stools or frequent stools <math>\geq 3</math> per 24 hours
 
• Wound: appropriate surgical site incision or wound with discharge, warmth, or erythema.
 
	Cough and a chest X-ray showing new infiltrate.
2. Positive cultures or other diagnostics with an MDRO.	
 
• Pulmonary: quantitative or semi-quantitative sputum or bronchoscopic cultures
 
• Urinary: <math>\geq 10^5</math> CFU/mL growth.
 
• Bloodstream: growth of a recognized bloodstream pathogen from blood but not another site or growth of a NHSN commensal from blood but not another site.
 
	Sputum culture growing $>10^5$ CFU/ml of K. pneumoniae resistant to ceftriaxone.

- Stool: positive PCR for the *C. difficile* toxin B gene (Cepheid or BioFire) or positive toxin B EIA
- Wound: growth of aseptically obtained organisms.

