3. Initiation of targeted antibiotics within 24 hours.	Antibiotics showing non-susceptibility using standard CLSI breakpoints or appropriate empiric antibiotics initiated at the time of clinical suspicion/testing and continued for $\geq 3$ days or initiated within 24 hours following the availability of diagnostic testing showing a culture-proven infection.	Initiation of ceftriaxone when the X-ray was ordered; later changed to meropenem.
---	--	---

10.3.5. *Fecal SCFA levels.* The SCFAs butyrate, acetate, and propionate will be measured from whole stools on a 6490 triple quadrupole mass spectrometer and compared between intervention groups using the first stool sample produced after the Day 3 assessment. Patients who fail to produce a stool from Day 3 to 7 will be excluded from this analysis.

10.3.6. *Proportion of goal calories through ICU Days 3 and 7.* Proportion of goal calories consumed will be defined by manually extracting data from electronic nursing flow sheets. Intake during the intervention be calculated by multiplying enteral or oral feeding caloric content by the flow rate or percentage of meal consumption. A patient-specific calorie target will be calculated by a registered clinical dietician using the Mifflin-St. Jeor equation and the Penn State 2003b and 2010 equations, taking into consideration age, body mass index, ventilation status, and comorbidities. The proportion of goal calories consumed will then be calculated as observed nutritional intake divided by calorie target. Day 3 and Day 7 proportions will be compared between intervention groups.

10.3.7. *Length of ICU stay.* Length of ICU stay through Day 30 will be compared between treatment groups, with Fine and Grey methods used to adjust for death as a competing risk. Length of ICU stay will be measured from the first to the last set of recorded ICU vital signs.

10.3.8. *Length of hospital stay.* Similarly, length of hospital stay through Day 30 will be compared between treatment groups, again adjusting for death as a competing risk. Length of hospital stay will be measured from the first set of recorded ICU vital signs to the last set of hospital recorded vital signs.

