### 11.2. Inclusion criteria

- Medical ICU. Subjects will be newly admitted to one of two CUMC medical ICUs during the study enrollment period;
- Age. Subjects will be eighteen or more years old at the time of ICU admission;
- Sepsis. Subjects will meet criteria for sepsis with life-threatening organ dysfunction caused by infection (Sepsis-3 third international consensus definition, 2016). According to this definition, life-threatening organ dysfunction is operationalized as an increase in the Sequential [Sepsis-Related] Organ Failure Assessment (SOFA) score of  $\geq 2$  points above baseline. Sepsis-3 criteria also require patients to have a known or suspected infection, defined as sampling of blood or any other body fluid for infection with concurrent administration of appropriate antibiotics (see Table 4);
- Appropriate antibiotics. Subjects will receive appropriate antibiotics, which will be operationalized as (1) among subjects with positive culture data, the antibiotics within classes where the organism is susceptible based on standard Clinical and Laboratory Standards Institute (CLSI) cut-offs; or (2) among subjects receiving empiric antibiotics (i.e., with negative cultures), antibiotics within classes with significant anaerobic activity. This will include  $\beta$ -lactam/ $\beta$ -lactamase inhibitor combination antibiotics, cephalosporins (generation 2 or greater), fluoroquinolones, lincosamides (clindamycin), metronidazole, and monobactams (a.g., meropenem). Vancomycin monotherapy is intentionally excluded. Antibiotics must be received within 24 hours before ICU admission or be actively ordered at the time of bedside screening;

- **Prompt intervention.** Subjects will complete study enrollment within 4 hours of ICU admission so that the intervention can be administered within 6 hours of ICU admission. The first set of recorded ICU vital signs will define the time of ICU admission.

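### The MDR infection outcome counts from ICU admission in patients enrolled with infection, and no rule excludes a presenting MDR infection cultured around Day 0

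*Combined protocol and SAP*

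**What the plan says.** Section 10.3.4 defines an MDR infection by three elements: site-specific signs, targeted antimicrobials started by the treating ICU team, and a culture or molecular test showing an MDRO. On the comparison it says: "Rates of infections will be compared between intervention groups as a sum total", and then separately for "the intervention period of Day 0 to 7, the Day 7 to 30 period, and the Day 30 to 6 month period".

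The clock starts at ICU admission. Section 11.2 states: "The first set of recorded ICU vital signs will define the time of ICU admission". Section 13 measures assessments from the same point.

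All subjects are infected or suspected to be infected at entry. Section 11.2 states: "Sepsis-3 criteria also require patients to have a known or suspected infection", with a body fluid sampled and antibiotics given.

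The third criterion of the adjudication table (the second table numbered 4) can be met by "appropriate empiric antibiotics initiated at the time of clinical suspicion/testing and continued for" at least 3 days.

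Treatment can begin well after the clock does. Section 9.4 says "it will be considered a protocol deviation if the intervention is administered more than 48 hours from ICU admission". Sections 9 and 11.2 give 6 hours, and these passages need to be reconciled.

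Section 15 records the date, suspected site and organism of each infection, but does not say which date is meant or how it is used. Section 17 gives no analysis for this outcome.

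**The concern.** A patient admitted with a resistant pneumonia or bloodstream infection, cultured on Day 0 and treated empirically, can satisfy all three criteria with the illness that led to enrollment. The table's own worked example reads like such a presentation: cough, a new infiltrate, empiric treatment when the film was ordered, a resistant organism, then a change of drug. The word *new* appears only in the pulmonary and stool items, each of which has an alternative that does not need it. It is absent from the urinary, bloodstream and wound items.

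The study product cannot prevent an infection that is already present. Counting it adds events unrelated to allocation to every arm, on the outcome named in the trial's title and short-term goal. The same infections also enter the adverse event tables. Section 17.2 deals with baseline status for MDRO colonization through a stratified reanalysis, but infection has no counterpart.

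**Working it through.** **The plan's own figures.** The plan states no power or sample size for this outcome. Two related figures reproduce:
- Section 9.2.1 reports that "84/126 (67%) new infections occurred within 3 days": 84/126 = 66.7%, and 97/126 = 77.0% within 7 days. This shows that events cluster early. It does not show that presenting infections are counted.
- The power formula used below (two-proportion z-test) gives 80.1% for 42% v 20.4% (30 v 60) and 80.1% for 42% v 17.3% (30 v 30), both at one-sided alpha 0.10. Section 17.3 states 80% for each.

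**Inputs.**
- New MDR infection on placebo, p0 = 0.21: the Cohort #1 figure in section 6.1, used here as an assumed rate of new infection.
- True risk ratio 0.50, so p1 = 0.105: assumed.
- Share of patients entering with a counted MDR infection, q = 0.10, 0.20 or 0.30: assumed, because the documents do not give it.
- Two-sided alpha 0.05: section 17.1.
- 30 per arm: section 17.3.

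**Model.** Count a patient once if any event occurs. Because q precedes treatment, its expectation is the same in all arms.

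Counted risk = q + (1 − q)p. The risk difference shrinks by the factor (1 − q).

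| q | Placebo | Inulin | Risk difference | RR | Power 60 v 30 | Power 30 v 30 |
|---|---|---|---|---|---|---|
| 0 | 0.210 | 0.105 | 0.105 | 0.50 | 29% | 20% |
| 0.10 | 0.10 + 0.90 × 0.21 = 0.289 | 0.10 + 0.90 × 0.105 = 0.195 | 0.095 | 0.67 | 18% | 13% |
| 0.20 | 0.20 + 0.80 × 0.21 = 0.368 | 0.20 + 0.80 × 0.105 = 0.284 | 0.084 | 0.77 | 13% | 10% |
| 0.30 | 0.30 + 0.70 × 0.21 = 0.447 | 0.30 + 0.70 × 0.105 = 0.374 | 0.074 | 0.84 | 10% | 8% |

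**If 21% already includes presenting infections.** Hold the counted placebo risk at 21%, let a share of those events be presenting ones, and keep the true RR at 0.50. At 60 v 30:

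| Presenting share of placebo events | RR as written | Power as written | Power, new infections only |
|---|---|---|---|
| 25% | 0.62 | 17% | 24% |
| 50% | 0.75 | 10% | 19% |
| 67% | 0.84 | 6% | 15% |

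The 67% row is an upper bound borrowed from the within-3-day share, which the protocol itself describes as new infections.

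**If infections are counted as events per patient.** A presenting infection then does not preclude a later one, and the counted rate is q + p. The difference stays at 0.105 in expectation. The ratio (q + 0.105)/(q + 0.21) is 0.205/0.31 = 0.66, 0.305/0.41 = 0.74 and 0.405/0.51 = 0.79 for the three values of q. The ratio still moves toward 1, and the added events add noise.

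**The case against.** A reader might infer that adjudicators are bound to count every presenting MDR infection. The documents do not support that. Section 10.3.4 requires the treating ICU team to have started the targeted antimicrobials, while section 11.2 admits patients whose antibiotics were given in the 24 hours before ICU admission. An infection dated before ICU admission also falls outside a window opening on Day 0. What stands is narrower: an MDR infection cultured around Day 0 and treated by the ICU team meets the criteria, and nothing stated excludes it.

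The authors may intend new infections only. Section 9.2.1 uses that term, section 6.1 says cohort patients developed infections, section 15 restricts AE reporting to dosed patients, and the definition is one the group has used before. That is plausible, but no onset rule is written in this protocol.

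A reader might also take the section 5.1 remark on ICU infections, "where over half of all infections are MDR", as the size of the problem. It describes ICU infections in general. It is not the share of these patients who enter with an infection meeting the adjudication table, so q stays an assumption.

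The consequences are limited. This is one of eleven additional outcomes and carries no power claim. Power is only 29% even without contamination under the assumed effect. Pooling the inulin arms is planned only for the primary and secondary outcomes, so 30 v 30 may be the relevant comparison. Section 17.2 takes the effect size for future trials from Day 3 colonization. All of this stands and bears on weight, but it does not supply the missing rule.

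**Conclusion.** The concern holds in limited form. As written, 10.3.4 can admit presenting MDR infections that treatment cannot affect, and it gives no basis for excluding those cultured around Day 0. The expected effect is to pull the ratio toward 1 in the sum total and the Day 0 to 7 period. With 30 per arm, chance imbalance at entry could shift a single result in either direction, so the bias should not be read as certain to hide a benefit. The Day 7 to 30 and later periods are largely unaffected, and the primary and secondary outcomes are untouched.

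The size is unknown. The calculated risk ratios and power figures depend on an assumed presenting share and an assumed halving of new infections. They illustrate the mechanism and do not estimate what this trial will see. The change is worth making before unblinding because infection is central to the trial's stated purpose and the rule is cheap to write.

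**What to change.** In 10.3.4 and its adjudication table, define an outcome infection as one whose first positive specimen is collected after randomization and which is not the enrolling infection. Randomization is a better anchor than first dose because randomized patients who are never dosed then still have a start point. An infection with the same organism at the same site as the enrolling one should count only if blinded adjudication finds a new episode under an interval rule stated in advance. Without that provision, a genuine recurrence during the 6-month follow-up could never count.

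Record presenting MDR infection as a baseline variable and report it by arm. Keep the count of all infections from Day 0 as a sensitivity analysis. State in section 15 whether the recorded infection date is that of onset, specimen or result.

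The cost is fewer counted events and a little more adjudication. Date, site and organism are already collected under section 15.

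### Criterion 3 of the MDR-infection definition describes the qualifying antibiotic as one the isolate is not susceptible to, which contradicts section 11.2 and the row's own heading

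*Combined protocol and SAP*

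**What the plan says.** Section 10.3.4 defines a culture-proven MDR infection by three elements, all required: site-specific signs, targeted treatment, and a culture or other diagnostic showing an MDRO. The running text gives the treatment element as item "2) initiation of targeted antimicrobials by the treating ICU team". The adjudication table in the same section (labelled Table 4, a number also used for the product table in 9.1) makes it criterion 3, headed "Initiation of targeted antibiotics within 24 hours". It defines the drug as "Antibiotics showing non-susceptibility using standard CLSI breakpoints or appropriate empiric antibiotics initiated at the time of clinical suspicion/testing". Two timing routes follow: a start at suspicion with at least 3 days of continuation, or a drug "initiated within 24 hours following the availability of diagnostic testing showing a culture-proven infection".

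The example for criterion 3 is "Initiation of ceftriaxone when the X-ray was ordered; later changed to meropenem". The example isolate for criterion 2 is "resistant to ceftriaxone".

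Section 11.2 defines appropriate antibiotics, for subjects with positive cultures, as "the antibiotics within classes where the organism is susceptible based on standard Clinical and Laboratory Standards Institute (CLSI) cut-offs". Its sepsis criterion also refers the reader to Table 4 for appropriate antibiotics.

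Sections 10.3.2 and 15 treat infections as both an outcome and a pre-specified adverse event, classified as MDR or not by these criteria.

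**The concern.** When every criterion is required, a fault in one of them decides whether an event exists. Here the drug is described in the opposite direction to section 11.2 and to what targeted treatment ordinarily means. An adjudicator applying the row as printed could accept an infection treated only with a drug the organism resists. The same adjudicator would have no clear basis for accepting one treated with an active drug once the result was known.

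Two smaller problems sit in the same row. Both timing routes, and the running text, require something to be started, although every subject enters with antibiotics given or ordered. The empiric route also needs 3 days of treatment, which a patient who dies sooner cannot supply. MDR infection is the event named in the trial's title and feeds the safety reports, so its definition should be unambiguous before anyone adjudicates.

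**Working it through.** **Step 1. Is there a design figure to reproduce?** No. The protocol gives no event count, sample size or power for this outcome, so the check is mainly textual.

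**Step 2. The four descriptions of the drug, side by side.**
- Running text of 10.3.4: targeted; started by the treating ICU team; no time limit.
- Row heading: targeted; started within 24 hours.
- Row body: isolate non-susceptible by CLSI breakpoints, or appropriate empiric therapy.
- Section 11.2: organism susceptible by CLSI cut-offs.

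The row body is the only one that points to resistance. The example does not settle the matter: the isolate resists the first drug, a second replaces it, and the table does not say which drug or which start time satisfies the criterion. The ICU-team phrase is also awkward, because 10.3.4 compares infections from Day 30 to 6 months, when many subjects will have left the ICU.

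**Step 3. Cases run through criterion 3.** Assume that signs and an MDRO are present.

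| Case | As printed | If the drug must be one the isolate is susceptible to |
|---|---|---|
| Inactive drug only, started at suspicion, kept at least 3 days | Met | Not met |
| Active drug first started within 24 h of the result | Timing met; drug is neither non-susceptible nor empiric, so unclear | Met |
| Inactive drug at suspicion, switched to an active one within 24 h of the result | Timing met; unclear which drug counts | Met by the second drug |
| Active empiric drug at suspicion, kept at least 3 days | Met by the empiric branch | Met |
| Active empiric drug at suspicion, death before 3 days and before the result | Not met | Not met without an until-death clause |
| Active drug already running for an earlier reason, left unchanged | Not met: no start | Not met: no start |

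Rows 1 to 3 are the drug-description fault. Rows 5 and 6 are the narrower timing gaps.

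**Step 4. C. difficile.** The table accepts a toxin B gene PCR or toxin EIA as the diagnostic. Neither yields an isolate with a breakpoint, so a susceptibility rule cannot be applied without a separate clause.

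**Step 5. Who is exposed to the early-death gap?** Section 12 (Retention) reports 11.3% mortality within 3 days in the group's cohorts. Those patients are replaced for the Day 3 analysis, but section 15 reports adverse events for everyone who received at least one dose. The share of such deaths involving an MDR infection is not given.

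**Step 6. What could this outcome detect in any case?** Illustration only. Take the 21% rate from Cohort #1 (section 6.1) for placebo, *assume* a halving to 10.5%, and compare 30 placebo with 60 combined inulin subjects at two-sided 0.05.
- Pooled rate = (30 × 0.21 + 60 × 0.105)/90 = 0.14.
- Null SE = √(0.14 × 0.86 × (1/30 + 1/60)) = 0.0776.
- Alternative SE = √(0.21 × 0.79/30 + 0.105 × 0.895/60) = 0.0842.
- z = (0.105 − 1.96 × 0.0776)/0.0842 = −0.56, so power is about 29%.

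The comparison is weak even with no misclassification at all.

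**The case against.** The strongest reply is that the drug wording is a drafting slip whose meaning can be recovered. The heading and running text both say targeted, section 11.2 defines appropriate therapy by susceptibility, and the example ends on a changed drug. Signs and an MDRO are still required, so an inactive drug cannot create an event by itself. The two kinds of error push the count in opposite directions, and no net bias is shown. The outcome is fourth of eleven additional ones, and patients, treating team and study team are blinded (12.1), so misclassification should be largely non-differential. All of that stands and limits the consequence. It does not remove the contradiction, because the table is the operational text that adjudicators will use.

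The requirement for a start also has a real defence. With 42% MDRO colonization in the group's cohort (17.3) and antibiotics in every subject at entry, asking for a new treatment decision helps separate infection from colonization. That stands too, and is why the main rule should keep it.

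Two stronger readings are tempting and are not supported.

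- *A reader might infer that MDR infections arising in patients already on broad-spectrum antibiotics are generally missed.* They are not. A new drug or a switch within 24 hours of the result meets the timing rule, and so does empiric therapy started at suspicion and kept for 3 days. Only infections with no qualifying start, or with death before either route can be completed, fall outside.
- *A reader might put a size on the loss:* 0.21 × 90 = 18.9 events; the protocol's timing, "84/126 (67%) new infections occurred within 3 days and 97/126 (77%) within 7 days", gives 18.9 × 84/126 = 12.6 by Day 3; an assumed 20–50% already covered gives 2.5 to 6.3 lost, or 13–33% of 18.9. This fails three times. Section 10.3.4 says the group used these criteria before and cites reference 40, which is also the source for Cohort #1, so the 21% is already net of any such loss. The timing figure is for new infections and is not said to be for MDR ones; 126 is also twice the roughly 63 patients that 21% of 301 gives, although one counts infections and the other patients. The 20–50% share has no source in the documents.

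**Conclusion.** The contradiction is real and needs no estimate to establish it: the row body of criterion 3 runs against section 11.2 and against its own heading. In a definition where every criterion must be met, it leaves the status of some MDR infections wrong or undetermined, both as an additional outcome and as a pre-specified adverse event. The gaps for an unchanged active regimen and for early death are genuine but narrower.

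Neither the number nor the net direction of misclassified events can be derived from the documents. The expectation that errors are similar across arms rests on randomization and blinding holding. The primary and secondary outcomes are untouched. This is a wording correction that should be made before adjudication; it is not a threat to the trial's main conclusions.

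**What to change.** Before any event is adjudicated:

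1. Reconcile the running text of 10.3.4, criterion 3 of its table, and section 11.2. The qualifying antibiotic should be one to which the isolate is susceptible by CLSI breakpoints. Remove the reference to non-susceptibility, state which drug and which start time satisfy the rule in the worked example, and align the 24-hour limit and the ICU-team phrase between text and table.
2. Add a separate clause for C. difficile diagnosed by PCR or EIA.
3. Let the 3-day continuation requirement be met by treatment until death if that comes sooner. A patient who dies before the result on an inactive drug would still fall outside; list such cases descriptively.
4. Keep the initiation rule in the main definition. Add a blinded sensitivity count, applied identically in all arms, that also accepts continuation of an already running active drug.

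Items 1 to 3 change a table row and a sentence or two. The inputs should be at hand: section 15 records date, site, organism and antibiotics for each infection, section 13.3 records antibiotic names, and MDR classification already needs the susceptibility result. Item 4 costs some extra adjudication and gives lower specificity against colonization, which is why it belongs in a sensitivity count. All of this concerns how events are classified; it implies nothing about which treatment patients should receive.
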